7.1 Adverse events

[figure not shown]
An adverse event (AE) is any untoward medical occurrence (i.e., any unfavorable and unintended sign [including abnormal laboratory findings], symptom or disease) in a subject or clinical investigation subject. Therefore, an AE may or may not be temporally or causally associated with the use of a medicinal (investigational) product.

All patients who have signed informed consent and are entered into the study will have all adverse events occurring after informed consent is signed recorded on the Adverse Event eCRF.

Pre-existing medical conditions/diseases (i.e., Medical History) are considered AEs if they worsen after providing written informed consent. Abnormal laboratory values or test results constitute AEs only if they induce clinical signs or symptoms, or are considered clinically significant, or they require therapy.

The occurrence of adverse events should be sought by non-directive questioning of the subject at each visit during the study. Adverse events also may be detected when they are volunteered by the subject during or between visits or through physical examination, laboratory test, or other assessments.

Clinically significant abnormal laboratory values or test results should be identified through a review of values outside of normal ranges/clinically notable ranges, significant changes from baseline or the previous visit, or values which are considered to be non-typical in patients with underlying disease. Investigators have the responsibility for managing the safety of individual subject and identifying adverse events. Alert ranges for liver related events are included in [Appendix 1](#).

Adverse events must be recorded on the Adverse Events eCRF under the signs, symptoms or diagnosis associated with them, and accompanied by the following information:

1. the severity grade (mild, moderate, severe)
 - mild: usually transient in nature and generally not interfering with normal activities
 - moderate: sufficiently discomforting to interfere with normal activities
 - severe: prevents normal activities
2. its relationship to the study treatment (no/yes), or investigational treatment (no/yes), or other study treatment (non-investigational) (no/yes), or both or indistinguishable,
3. its outcome, or if the event is ongoing an outcome of not recovered/not resolved should be reported.
4. whether it constitutes a serious adverse event (SAE)
5. action taken regarding study treatment

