7.2 Serious adverse event reporting

To ensure subject safety, every SAE, regardless of causality, occurring after the subject has provided informed consent and until 30 days after the last study visit must be reported to Novartis within 24 hours of learning of its occurrence.

Any SAEs experienced after the 30 days period should only be reported to Novartis if the investigator suspects a causal relationship to study treatment.

Recurrent episodes, complications, or progression of the initial SAE must be reported as follow-up to the original episode, regardless of when the event occurs. This report must be submitted within 24 hours of the investigator receiving the follow-up information. An SAE that is considered completely unrelated to a previously reported one should be reported separately as a new event.

Information about all SAEs (either initial or follow up information) is collected and recorded in English on the paper Serious Adverse Event Report Form. Study site personnel must also inform the Novartis Medical Expert and/or Global Trial Leader. The Investigator must assess the relationship to each specific component of the study treatment (if the study treatment consists of several components).

SAEs (initial and follow-up) should be faxed within 24 hours of awareness of the SAE to the local Novartis Drug Safety and Epidemiology Department. The telephone and fax numbers of the contact persons in the local Drug Safety and Epidemiology department, specific to the site in the investigator folder provided to each site. The original copy of the SAE Report Form and the fax confirmation sheet must be kept with the case report form documentation at the study site. Follow-up information should be provided using a new paper SAE Report Form stating that this is a follow-up to a previously reported SAE.

Follow-up information provided should describe whether the event has resolved or continues, if and how it was treated, whether the treatment code was broken or not and whether the subject continued or withdrew from study participation.

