### Adverse events

Summaries will be provided for:

- Adverse events by SOC and PT

- Adverse events by severity
- Treatment emergent adverse events (Population I only)
- Post-treatment adverse events (Population II only)
- Death

█ [REDACTED]  
Adverse events of special interest (AESI)

Summary by treatment group in this study will be provided for Populations I and II separately.

All by-patient data listings will be sorted by Population, treatment group, center and patient if not indicated otherwise.

Adverse events continuing from the core study but not worsening in severity during the extension, will also be entered in the extension study database. These adverse events, will be presented in the listings but not in the tables. Adverse events continuing from the core study, but worsening in severity during the extension, will be entered as new events in the database and will be included in both tables and figures.

In addition to summary tables, safety topics of interest such as: cardiovascular events spontaneous muscle contractions; diarrhea and diarrhea-like events defined in the Safety Profiling Plan (SPP) will be listed separately.

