### **Treatment emergent adverse events**

Adverse events will be deemed treatment-emergent if events started after the first dose of study treatment or events present prior to the first dose of study treatment but increased in severity, until 56 days after the last dose of study treatment. For Population II, the dose received at Core Week 21 visit is the scheduled last dose. For patient entering the extension study, their last visit in the core study is Week 25, which is the first visit in the extension study. Therefore, treatment emergent adverse events after Week 25 (Core EOT) are collected in the extension study. Such treatment emergent adverse events cannot be identified completely based on extension study database alone, therefore cannot be summarized with accuracy. .

Treatment emergent adverse events will be summarized for population I. Only primary paths within MedDRA (SOC) will be considered for adverse event reporting.

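### A core-study adverse event that first becomes serious or fatal after Week 25, under the same term and severity grade, is left out of the extension AE and SAE tables

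*SAP*

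**What the plan says.** Protocol 6.1.2 requires every adverse event ongoing at the core Week 25 visit to be recorded again in the extension eCRF. SAP 3.6.1.2, under Adverse events, then separates these carried-over events by one criterion, a change in severity.

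- Without a change: "Adverse events continuing from the core study but not worsening in severity during the extension, will also be entered in the extension study database". For these, "These adverse events, will be presented in the listings but not in the tables".
- With a change: "Adverse events continuing from the core study, but worsening in severity during the extension, will be entered as new events in the database", and they are then included in the summaries.

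The SAP's treatment-emergent definition, summarised for Population I, applies the same test to pre-existing events. It counts "events present prior to the first dose of study treatment but increased in severity".

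Protocol 7.1 lists severity and seriousness as separate items on the adverse event record. Severity has three grades, and the top one reads "severe: prevents normal activities". Seriousness has its own criteria, among them death, threat to life, disability and hospitalization.

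**The concern.** Severity grade decides which carried-over events are counted, including in the SAE tables, yet those tables are about seriousness. The two can move independently. An event can lead to hospital admission without a change of grade. An event already at the top grade has no higher grade to reach.

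The evaluation of long-term safety after treatment withdrawal is a secondary objective (Protocol 2.2, SAP 2.1). Events that began during core treatment and turned serious during the off-drug follow-up bear directly on it. A table of serious events in the extension that omits them by rule gives too low a count, and a reader of the table alone would not know.

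**Working it through.** No arithmetic applies. The plan gives no figure for events ongoing at Week 25, so the check is to follow a carried-over event through each rule.

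**Step 1: does the change belong to the extension?** Yes. The SAP's treatment-emergent section says that Week 25 is the last core visit for patients who enter the extension, and that later events are collected in the extension. A change at, say, Week 35 is extension data.

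**Step 2: does the tabulation trigger fire?**

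| Carried-over event at Week 25 | What happens in the extension | Grade rises? | Where it appears |
|---|---|---|---|
| Moderate, not serious | Becomes severe and serious | Yes | New event, tabulated |
| Moderate, not serious | Hospitalization, still graded moderate | No | Listing only |
| Severe, not serious | Becomes life-threatening, same term | Cannot rise | Listing only |
| Severe, not serious | Fatal, same term | Cannot rise | AE listing and death listing |
| Any grade | Complication entered under its own diagnosis | Not applicable | New event, tabulated |

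The three middle rows are the gap.

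**Step 3: does another rule bring these events back?**

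- *SAE tables.* The SAP plans summaries of serious, treatment-emergent serious (Population I) and post-treatment serious (Population II) events by system organ class and preferred term. It states no exception to the carried-over rule.
- *Treatment-emergent definition.* For pre-existing events it uses the same severity-only test.
- *Post-treatment definition.* It refers to onset or worsening without tying worsening to severity. The SAP then says such events cannot be identified accurately from the extension database. It uses two intervals based on the event's start date instead: Week 25 to Week 25 plus 35 days, and Week 25 plus 36 days onward. A carried-over event that is not entered as new keeps a start date before Week 25 and falls in neither interval. For Population II this is a second, separate exclusion.
- *Deaths.* The SAP lists all deaths. It names death among the summaries to be provided, but its Deaths section makes the table optional. A non-fatal event that becomes serious has no equivalent provision.

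None of these rules restores a same-term, same-grade event that becomes serious after Week 25 to the AE or SAE tables.

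**The case against.** Several counter-arguments have force.

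- *Nothing is lost.* The events remain in the by-patient listings, SAEs go to the sponsor within 24 hours, the data monitoring committee sees unblinded safety data, and specified cardiac events are adjudicated. This stands. The gap is in tabulation, not in collection or oversight.
- *Some cases will be captured anyway.* A complication with its own diagnosis can be entered as a new event and tabulated. This also stands, and it limits the point to events kept under the same term and grade. How sites record a continuing event whose status changes depends on completion guidelines that are not in the documents.
- *Few events may be involved.* Entrants must have completed core treatment and must have no condition that should have stopped it. Severe events still ongoing at Week 25 are plausibly uncommon. It is true by definition that no event already graded severe can trigger the rule, but that says nothing about frequency.
- *The severity test comes from the protocol.* Protocol 9.5.2 defines treatment-emergent pre-existing events by increased severity. This is correct for that definition, and it means a SAP-only edit there would depart from the protocol. The rule that keeps unchanged carried-over events out of all tables is in the SAP.
- *Not everything is visible.* The SAP's list of summaries has a redacted entry, and the Safety Profiling Plan and programming specifications are separate documents. This calls for some caution about absence from every table, but it does not change the stated rule.

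A reader might also infer that Protocol 7.2 widens the gap, because it says: "Recurrent episodes, complications, or progression of the initial SAE must be reported as follow-up to the original episode, regardless of when the event occurs". The documents do not support that reading. The sentence governs SAE reports to the sponsor, not the derivation of tables. It also applies to an event that is already serious, not to one that becomes serious for the first time.

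**Conclusion.** The concern holds for a defined class: a core event carried over at Week 25, kept under the same term and grade, that first becomes serious or fatal during the extension. Followed as written, the SAP leaves such an event out of the extension AE and SAE tables. This is a rule that yields a wrong count for a stated safety objective, not merely a missing detail. It is worth correcting before database lock.

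The size cannot be derived. The documents do not say how many events were ongoing at Week 25 or how many might change status, and the number may be small.

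A reader might infer that the omission hides more serious events in the bimagrumab arms than in placebo. That would require more ongoing events at Week 25 in those arms, and the documents give no information on this. Neither a direction of bias nor an effect on any arm's SAE rate can be claimed.

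The conclusion assumes that the redacted entry and the separate specifications do not already add a seriousness trigger.

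**What to change.** In SAP 3.6.1.2, under Adverse events, add a second route into the tables. A carried-over core event is also included in the AE and SAE tables if, on or after the Week 25 visit, it first meets a seriousness criterion or has a fatal outcome. Identify these events by comparing the seriousness and outcome on the extension record with those on the core record.

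For the Population II intervals, use the date on which the event became serious. The items that Protocol 7.1 lists for the adverse event record do not include this date. It would have to come from the SAE form or the safety database, and the sponsor should first confirm that it is available. If it is not, show these events in a separate row of the table rather than in an interval.

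For Population I there are two acceptable courses. One is to leave the treatment-emergent definition as it is, in line with Protocol 9.5.2, and show these events separately. The other is to extend the definition and document it as a change from the protocol.

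The cost is a short addition to the SAP and some linkage to core and SAE-form data. SAE counts may rise slightly. Efficacy analyses and patient management are unaffected.

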### **Adverse events by SOC and PT**

The number (n) and percentage (%) of patients with adverse events will be summarized by primary SOC, PT and treatment group. Unless otherwise specified, primary system organ classes will be sorted by descending order of total frequency and within each primary system organ class, the preferred terms will be sorted by descending order of total frequency as well. In the event of SOCs and/or PTs with equal total frequencies, the relevant SOCs and/or PTs will be sorted alphabetically. A subject with multiple adverse events within a SOC or PT is only counted once towards the total of this SOC or PT.

Separate summaries will be provided by SOC and PT for:

- Adverse events
- Treatment emergent adverse events (Population I only)
- Post-treatment adverse events (Population II only)
- Serious adverse events
- Treatment emergent serious adverse events (Population I only)
- Post-treatment serious adverse events (Population II only)
- Other significant adverse events leading to discontinuation of study treatment
- And adverse events leading to dose interruption (including study treatment discontinuation) (Population I).

### **Adverse events by severity**

The number (n) and percentage (%) of patients with adverse events will be summarized by severity, primary system organ class, PT and treatment group. If a patient reported more than

one adverse event with the same PT, the adverse event with the greatest (maximum) severity will be presented. If a patient reports more than one adverse event within the same primary system organ class, only one adverse event will be counted for that patient at the highest severity level in the total row for each primary system organ class. If adverse event “severity” is missing, this variable will be listed as missing and treated as missing in summaries.

Separate summaries will be provided for:

- Adverse events
- Treatment emergent adverse events (Population I only)
- Post-treatment adverse events (Population II only)

### **Treatment emergent adverse events**

Adverse events will be deemed treatment-emergent if events started after the first dose of study treatment or events present prior to the first dose of study treatment but increased in severity, until 56 days after the last dose of study treatment. For Population II, the dose received at Core Week 21 visit is the scheduled last dose. For patient entering the extension study, their last visit in the core study is Week 25, which is the first visit in the extension study. Therefore, treatment emergent adverse events after Week 25 (Core EOT) are collected in the extension study. Such treatment emergent adverse events cannot be identified completely based on extension study database alone, therefore cannot be summarized with accuracy. .

Treatment emergent adverse events will be summarized for population I. Only primary paths within MedDRA (SOC) will be considered for adverse event reporting.

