5.5 Treating the patient

5.5.1 Patient numbering

Patients in the extension study CBYM338E2202E1 will continue with the same uniquely identified patient number that was assigned in the core study.

As in the core study, the patient number is a combination of a four digit center number, which is provided by Novartis, and a three digit sequential number allocated by the investigator, starting with 001. Therefore, if the center number is 1001, the patient numbers will be assigned such as 1001001, 1001002, etc. in ascending order. If the center number is 1002, the patient numbers will be assigned such as 1002001, 1002002, etc.

Patients will be given the informed consent form (ICF) during one of the scheduled visits (e.g., Week 25 or at earlier visit) in study CBYM338E2202 to read and understand for their participation in this extension study. Patients will NOT be signing the ICF before completing the Week 25 (EOT) assessments of the core study.

Patients who are eligible based on the inclusion/exclusion criteria will be asked to sign the ICF. If the patient fails for any reason, he/she should not enter the extension and should complete the EoS visit of the core study as per the core study protocol.

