9.5.2 Safety variables

All safety evaluations will be performed on the safety set (SAF) and analyzed for Population I and Population II separately. For Population I, all safety will be summarized by treatment group assigned in this extension study. Safety will be compared between the 3 continued bimagrumab dose arms against the placebo arm continued from the core study. For Population II, safety analysis will be presented by the treatment assigned in the Core study.

Adverse events

Treatment emergent adverse events (events started after the first dose of study treatment or events present prior to the first dose of study treatment but increased in severity based on preferred term) will be summarized. Only primary paths within MedDRA will be considered for adverse event reporting.

Summary by treatment group in this study will be provided for Populations I and II separately.

AEs will be summarized by presenting, for each treatment group, the number and percentage of subjects having any AE, having an AE in each primary system organ class and having each individual AE (preferred term). Summaries will also be presented for AEs by severity and for study treatment related AEs. If a subject reported more than one adverse event with the same preferred term, the adverse event with the greatest severity will be presented. If a subject reported more than one adverse event within the same primary system organ class, the subject will be counted only once with the greatest severity at the system organ class level, where applicable.

Separate summaries will be provided for death, serious adverse event, other significant adverse events leading to discontinuation of study treatment and adverse events leading to dose adjustment (including study treatment discontinuation).

Safety topics of interest such as cardiovascular events defined in the Safety Profiling Plan will be listed and analyzed separately.

[REDACTED]

Vital signs

Summary statistics in vital signs for each visit will be presented by vital sign and treatment group for Populations I and II separately.

All information collected will be listed by subject and abnormal values will be flagged.

Laboratory data

The summary of laboratory evaluations will be presented for the following groups of laboratory tests (see respective sections for details) for Populations I and II separately:

- Hematology
- Clinical chemistry

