### **Post-treatment adverse events**

Adverse events with date of onset or worsening after the date of last infusion of study drug + 56 days are considered as post-treatment adverse events.

Based on the extension study database alone, the post-treatment adverse events will not be identified accurately according to above definition. Also, to take into consideration that adverse events starting between Week 25 and Week 29 could potentially fall into the definition of treatment emergent adverse events, adverse events of population II will be summarized by time interval, with adverse events starting date in the interval of:

- Week 25 to Week 25 + 35 days
- Week 25 + 36 days onward

The summary will be done for Population II only.

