## 5.4 Definition of Baseline and post-baseline measurements

Baseline is defined as the core study baseline, for both populations. In the planned analyses, Week 25 has been referred to majority of the time, and it is referring to a relative baseline to the extension study, which is defined as the Visit 1 pre-dose assessments of the extension study (Week 25, EOT visit of the core study) for population I and for population II defined as the Visit 1 assessments of the extension study (Week 25, EOT visit of the core). This visit will be labeled as Week 25 in the reports.

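### For Population II the SAP sets aside its own 56-day adverse event rule for a fixed split at Week 25 + 35 days, although core last-infusion dates would let the rule be applied

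*SAP*

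**What the plan says.** SAP 3.6.1.2 (Treatment emergent adverse events) covers events that start after the first dose, and events already present that "increased in severity, until 56 days after the last dose of study treatment". The next heading, Post-treatment adverse events, is the complement: events with onset or worsening "after the date of last infusion of study drug + 56 days are considered as post-treatment adverse events".

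For Population II the SAP notes that "For Population II, the dose received at Core Week 21 visit is the scheduled last dose", so the end of the 56-day period falls inside the extension. It then gives its reason for not applying the rule: "Such treatment emergent adverse events cannot be identified completely based on extension study database alone". The same reason is repeated for post-treatment events. Treatment-emergent tables are limited to Population I. Population II events are grouped by start date into "Week 25 to Week 25 + 35 days" and a second interval from day 36 onward.

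The output lists in SAP 3.6.1.2 (Adverse events, by SOC and PT, and by severity) nevertheless keep post-treatment adverse events for Population II, and the SOC and PT list also keeps post-treatment serious adverse events.

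On linkage, Protocol 5.5.1 says that extension patients "will continue with the same uniquely identified patient number that was assigned in the core study". SAP 5.4 says "Baseline is defined as the core study baseline, for both populations". SAP 3.1 admits a patient to the Safety Set on at least one dose in the core or the extension and analyses by treatment actually taken. Population II receives no investigational drug in the extension (Protocol 5.1.1), so for these patients both rest on core dosing.

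**The concern.** The rule needs one date per patient, that of the last core infusion. The SAP's only obstacle is that the extension database by itself is not enough. Nothing in either document says that the core date cannot be obtained, and other parts of the SAP need core information in any case.

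The substitute is also not derived. Beside the 35-day cut, the SAP explains that events between Week 25 and Week 29 might still count as treatment-emergent. That is a 28-day span, and the other 7 days are not explained.

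What is at stake is how clearly the tables separate residual-exposure events from off-drug events. Safety after treatment withdrawal is a secondary objective (Protocol 2.2), and Population II is most of the study: about 200 patients expected less about 45 enrolled before the amendment leaves about 155, or roughly 78%. There is also a programming problem. The listed post-treatment tables have a definition that the SAP says cannot be applied accurately, and it is unclear whether they should use that definition or the interval split.

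**Working it through.** **Inputs**
- Limit of the treatment-emergent period: 56 days after the last dose (SAP 3.6.1.2).
- Scheduled last dose for Population II: core Week 21 (SAP 3.6.1.2).
- Core end-of-treatment visit (Week 25): 4 weeks after the last dose (Protocol 3.1).
- SAP split: Week 25 + 35 days.

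**Formula.** Let g be the days from the last core infusion to the Week 25 visit. The 56-day limit is then Week 25 + (56 − g) days.

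**Can the 35 be reproduced?** On schedule, g = (25 − 21) × 7 = 28, so the limit is Week 25 + (56 − 28) = Week 25 + 28 days. This agrees with the SAP's mention of Week 29 but not with its split. The excess is 35 − 28 = 7 days, which is 7/35 = 20% of the 35 days after Week 25. A 3-day allowance gives +31 and a 14-day allowance gives +42. A 7-day allowance gives +35, but neither document states one.

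**Variation in g.** The core visit window is not in the documents, so the values of g other than 28 are assumptions. Post-treatment days in the early interval = 35 − (56 − g), and treatment-emergent days in the late interval = (56 − g) − 35, each not below 0. The last column repeats the second formula with a cut at +28, that is 28 − g, not below 0.

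| g (days) | 56-day limit | Post-treatment days in early interval | Treatment-emergent days in late interval | The same, with cut at +28 |
|---|---|---|---|---|
| 14 | Week 25 + 42 | 0 | 7 | 14 |
| 21 | Week 25 + 35 | 0 | 0 | 7 |
| 25 | Week 25 + 31 | 4 (11%) | 0 | 3 |
| 28 | Week 25 + 28 | 7 (20%) | 0 | 0 |
| 31 | Week 25 + 25 | 10 (29%) | 0 | 0 |
| 35 | Week 25 + 21 | 14 (40%) | 0 | 0 |

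Two results follow. No fixed offset from Week 25 matches the rule for every patient, whereas last infusion + 56 days does by construction. And the 35-day cut keeps the late interval free of treatment-emergent days whenever g is at least 21, which a 28-day cut does only when g is at least 28.

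**Is the last-infusion date the main missing item?** It appears so. Events continuing from the core that worsen are entered as new events in the extension database (SAP 3.6.1.2, Adverse events), so onset and worsening after Week 25 are already recorded there.

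**The case against.** The strongest reply is that the SAP discloses the limitation and replaces the rule with two plain time intervals. Neither is labelled on-treatment, so it would be wrong to infer that 20% of the early interval is misclassified. The SAP says only that early events might be treatment-emergent. This stands: the 7 days measure mixing of person-time, not wrongly labelled events.

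The later cut may also be deliberate. If the 3-day window that Protocol section 6 gives for pre-amendment patients is assumed at both the last dose and Week 25, g could be as low as 28 − 6 = 22. The limit is then Week 25 + 34, which 35 covers and 28 does not. The SAP does not give this reason, but it shows that 35 need not be a mistake. Moving the cut to 28 days would be a step backward.

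A reader might go further and suppose that a patient last dosed at core Week 17 (g = 56) spends all 35 days off treatment. The arithmetic is right, but the documents do not show that this can happen. Entry requires completing the core treatment period per protocol, Week 25 is set 4 weeks after the last dose, and the core missed-dose rules are not available here.

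A shared patient number makes linkage possible but does not prove that core dosing data sit in the reporting database. The core baseline in SAP 5.4 is weak support as well, since that section says that Week 25 is the reference most of the time. The Safety Set definition is the firmer ground.

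Finally, Protocol 9.5.2 says "Summary by treatment group in this study will be provided for Populations I and II separately". One might read this as a broken promise of treatment-emergent tables for Population II. The sentence requires separate summaries by population, which the SAP provides, and the protocol's treatment-emergent definition there has no 56-day limit. It does not carry the point.

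**Conclusion.** The point holds as a worthwhile and cheap improvement. The SAP has a patient-level rule, sets it aside for Population II for a reason that one core date would largely remove, and leaves listed post-treatment tables resting on a definition it says cannot be applied accurately. On schedule, the early interval combines 28 days of possible treatment-emergent time with 7 days that are post-treatment by the SAP's own rule. With assumed gaps of 21 to 35 days, the post-treatment part runs from 0 to 14 days.

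The conclusion rests on the core last-infusion date being obtainable, which the documents neither state nor deny. The gain in accuracy concerns the cut-off; events with incomplete dates still depend on imputation (SAP 5.7). The consequence is limited. All events still appear in the overall adverse event tables by core treatment, no test depends on the cut, and the late interval is already clean of treatment-emergent time for patients on schedule.

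**What to change.** 1. Import each Population II patient's core last-infusion date, matched by patient number, into the extension analysis data.
2. Classify each Population II event recorded in the extension as treatment-emergent (onset or worsening no more than 56 days after that date) or post-treatment (more than 56 days), using the imputed date where the recorded one is incomplete.
3. Use this classification for the Population II tables listed in SAP 3.6.1.2, including post-treatment serious events and the severity tables. If a treatment-emergent table is added, its title should say that it covers only events from Week 25 onward, since earlier ones belong to the core study.
4. Keep the Week 25 + 35 days split, if wanted, as a secondary display, and state why 35 days was chosen. Do not move it to 28 days.
5. If the core dates turn out not to be available, say so in the SAP and state which definition the listed post-treatment tables follow.

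The cost is one cross-study merge and revised SAP wording, with no new data collection. An infusion date need not reveal the assigned treatment, so blinding is not an evident obstacle.
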